## **9.0** **INVESTIGATIONAL PLAN**

### **9.1** **OVERALL STUDY DESIGN AND PLAN: DESCRIPTION**

Study RAP-MD-33 is a multicenter, randomized-withdrawal, parallel-group, placebo-controlled, maintenance study of rapastinel as monotherapy in adult patients with MDD who completed the RAP-MD-30, RAP-MD-31, or RAP-MD-32 DBTP. The final visit from the lead-in study (ie, Visit 9) will serve as Visit 1 in Study RAP-MD-33.

This study will be conducted in the following periods:

- An 8- to 16-week, Open-label Treatment Period (OLTP)
- A 52-week, DBTP, randomized-withdrawal period during which stable responders from the open-label period will be randomized (1:1:1) to 1 of 3 double-blind treatment arms:
  - Rapastinel weekly (IV, 450 mg or 225 mg)
  - Rapastinel clinically driven schedule (IV, 450 mg or 225 mg, variable interval, placebo on intervening weeks)
  - Placebo weekly (IV)
- A 2-week Safety Follow-up Period

Approximately 1400 patients are planned for enrollment in the OLTP to achieve approximately 600 randomized patients in the DBTP. When approximately 600 patients are randomized into the DBTP, enrollment in the OLTP will be closed.

A schematic of the study design is presented in [Figure 9.1.3–1](#). The Schedule of Evaluations is provided in [Section 2.0](#).

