#### **9.1.1** **Open-label Treatment Period**

Patients will enroll from Study RAP-MD-30, RAP-MD-31, or RAP-MD-32, and the final visit from that study (Visit 9/ET [Week 6]) will serve as Visit 1 in Study RAP-MD-33. Patients will be screened at Visit 1 and those who meet entry criteria will also enter the OLTP at Visit 1 and will receive the first dose of open-label treatment (rapastinel) at Visit 1 to ensure continuity of treatment.

The OLTP consists of weekly visits for at least 8 weeks (and up to 16 weeks). During this period, patients will be treated with weekly IV injections of rapastinel (450 mg or 225 mg). The dose assigned in the OLTP will be blinded and be based on the dose received in the lead-in study such that those who received placebo, vortioxetine, or 450 mg or 900 mg rapastinel in the lead-in study will be assigned 450 mg rapastinel, while those who received 225 mg rapastinel in the lead-in study will be assigned 225 mg rapastinel.

The purpose of this period is to identify stable responders who will be eligible for the randomized-withdrawal period.

Patients will be monitored through the OLTP stability assessment. A patient will be considered to have met OLTP stability criteria upon achieving both:

- MADRS total score  $\leq 12$  with no more than 1 modest MADRS excursion (MADRS  $> 12$  but  $\leq 16$ ) during 6 consecutive weeks, and
- MADRS total score  $\leq 12$  for 2 consecutive visits prior to randomization

Patients may meet OLTP stability assessment criteria at any point from Study Week 8 to Study Week 16.

Patients who do not meet stability criteria within these timeframes will undergo the End-of-Treatment/Early Termination assessments (Visit 69/Week 52/ET) at their last OLTP visit.

Patients who discontinue from Study RAP-MD-33 OLTP will enter a 2-week safety follow-up period.

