### **9.1.3 Safety Follow-up Period**

All patients who complete or discontinue from the study should enter the 2-week safety follow-up period.

Additional follow-up visits may be scheduled within 30 days, if necessary, for safety reasons.

A schematic of the study design is presented in [Figure 9.1.3–1](#). The Schedule of Evaluations is provided in [Section 2.0](#) and detailed descriptions of each study visit can be found in [Section 9.5.5](#).

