# 2.0 INTRODUCTION

This Statistical Analysis Plan (SAP) describes the methodology that will be used to summarize the statistical analyses of the efficacy and safety data for the final protocol of Study RAP-MD-33 (version dated 02MAY2018).

Study RAP-MD-33 is a Phase 3, multicenter, randomized-withdrawal, parallel-group, placebo-controlled, maintenance study to evaluate the efficacy, safety, and tolerability of rapastinel in the prevention of relapse in patients with major depressive disorder (MDD) who completed one of the rapastinel lead-in studies including RAP-MD-30 and RAP-MD-32. The RAP-MD-31 study was terminated before any patient was enrolled. Thus, there is no patient rolled-over from the RAP-MD-31 study to RAP-MD-33 study.

The study will be conducted in the following periods:

- An 8- to 16-week open-label treatment period (OLTP) where patients receive rapastinel 225 or 450 mg IV weekly
- A randomized double-blind treatment period (DBTP) of at most 52 weeks of treatment duration where patients are randomized 1:1:1 to either rapastinel 225 or 450 mg weekly, rapastinel clinically driven schedule (IV, 225 or 450 mg, variable interval, placebo on intervening weeks) or placebo
- A 2-week safety follow-up period

In order for patients to transition from the OLTP and be randomized into the DBTP, the patient must meet the stability criterion sometime after 8 weeks (and up to 16 weeks) during the OLTP. A patient will be considered a stable responder upon achieving both criteria (1) and (2) below:

- 1) An observed Montgomery-Asberg Depression Rating Scale (MADRS) total score  $\leq 12$  with no more than one modest MADRS excursion (MADRS total score > 12 but  $\leq 16$ ) for at least six consecutive weeks.
- 2) An observed MADRS total score  $\leq 12$  for at least two consecutive visits prior to randomization.

The OLTP starts with the first dose of open-label treatment and ends with one of the following: the first dose of double-blind treatment for patients who enter the DBTP or Visit 69/Week 52 End-of-Treatment/Early Termination (ET) assessments for patients who do not enter the DBTP.

The double-blind treatment period starts when the first dose of double-blind treatment is administered and ends when the patient meets relapse criteria, completes 52 weeks of double-blind treatment, or discontinues for other reasons.

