The safety follow-up (SFU) period starts after completion of the last scheduled assessment (or ET) and ends with the last available assessment.

Individual treatment durations will vary. The maximum duration of the study will be 70 weeks.

RAP-MD-33 Statistical Analysis Plan

RAP-MD-33 Statistical Analysis Plan

Page 10

Page 12

RAP-MD-33 Statistical Analysis Plan

Page 13

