An AE (classified by preferred term) that occurs during the SFU of the study will be considered a newly emergent adverse event (NEAE) if the AE was not present before or at Visit 70 or it was present before or at Visit 70 and increased in severity during the SFU. An AE that becomes serious during the SFU will also be considered as NEAE. If more than 1 AE is reported before or at Visit 70 and coded to the same preferred term, the AE with the greatest severity will be used as the benchmark for comparison with the AEs occurring during the SFU that were also coded to that preferred term.

An AE that occurs more than 30 days after the date of the last dose of IP will not be counted as an NEAE.

An SAE that occurred between the date of the first dose of IP in the OLTP and 30 days after the date of the last dose of IP, inclusive, will be considered a treatment-emergent SAE (e.g., TESAE).

The overall number and percentage of patients with TEAEs, NEAEs, death, TESAEs, TEAEs leading to study discontinuation and TEAEs related to study drug during the OLTP will be tabulated overall, and during the DBTP and the SFU by treatment group.

The incidence of common ( $\geq 2\%$  of patients in any treatment group) TEAEs and NEAEs during the OLTP will be summarized overall by preferred term. Similarly, the incidence of common TEAEs and NEAEs during the DBTP and during the SFU will be summarized by preferred term and treatment group and will be sorted by decreasing frequency starting with the weekly rapastinel group followed by the clinically driven schedule rapastinel group.

Listings will be presented for all patients with AEs and patients who died (if any).

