## **12.0 DETERMINATION OF SAMPLE SIZE**

The sample size and power calculations are based on the analysis of time to relapse during the first 52 weeks of the DBTP. Assuming a relapse rate of 19% per 26 weeks in the placebo group and a dropout rate of 20% per 26 weeks in all treatment groups, the sample size of 200 per group will have 90% power to detect a hazard ratio of 0.475 for a rapastinel treatment versus placebo at a 0.05 significance level. To achieve this number of randomized patients, approximately 1400 patients need to be enrolled in this study if 50% of patients are qualified for randomization.

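### SAP 9.1 gives never-randomized patients no summary column or denominator for adverse events in safety follow-up; these events appear only in listings

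*SAP*

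**What the plan says.** **Who enters follow-up.** Protocol 9.1.1: "Patients who discontinue from Study RAP-MD-33 OLTP will enter a 2-week safety follow-up period". Protocol 9.1.3 is wider: "All patients who complete or discontinue from the study should enter the 2-week safety follow-up period". Protocol 9.3.3 says the same of treated patients who stop prematurely.

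**Where the periods divide.** For patients who are not randomized, SAP 2.0 ends the open-label treatment period (OLTP) at "Visit 69/Week 52 End-of-Treatment/Early Termination (ET) assessments for patients who do not enter the DBTP". It continues: "The safety follow-up (SFU) period starts after completion of the last scheduled assessment (or ET) and ends with the last available assessment".

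**How events are summarized.** In SAP 9.1 the overall counts "during the OLTP will be tabulated overall, and during the DBTP and the SFU by treatment group". For common events, "the incidence of common TEAEs and NEAEs during the DBTP and during the SFU will be summarized by preferred term and treatment group", sorted by the weekly and then the clinically driven rapastinel group. Listings cover every patient with an adverse event and every death.

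**What counts as treatment-emergent.** SAP 9.1 keeps both TEAE and TESAE status open until 30 days after the last dose.

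**How many patients.** Protocol 9.1: "Approximately 1400 patients are planned for enrollment in the OLTP to achieve approximately 600 randomized patients in the DBTP". SAP 12.0: "approximately 1400 patients need to be enrolled in this study if 50% of patients are qualified for randomization".

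**The concern.** A patient who is never randomized belongs to no double-blind arm. If the safety follow-up (SFU) tables have only the double-blind arms as columns, that patient's events after the ET visit fall outside the OLTP (already closed), outside the double-blind treatment period (DBTP, never entered), and outside every SFU column.

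These patients all last received open-label rapastinel, and by plan they are at least half of those enrolled. Some will have been withdrawn during the OLTP under the suicide-related criteria of Protocol 9.3.3.1. The SAP's own definitions class their events as treatment-emergent up to 30 days after the last dose. A listing shows each event but gives no count over a denominator, so a reader of the report could not state a follow-up event rate for patients coming off open-label treatment.

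**Working it through.** **Step 1. Trace a never-randomized patient through the SAP.**

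| Time of event | Period under SAP 2.0 | Summary under SAP 9.1 |
|---|---|---|
| First open-label dose to Visit 69/ET | OLTP | Tabulated overall |
| After Visit 69/ET | SFU | By treatment group only |

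The second row has no cell for this patient if treatment group means double-blind arm.

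**Step 2. Does it mean that?** The sentence in SAP 9.1 does not contain the word double-blind. Three places point to it:
- The common-event table is sorted by the weekly and clinically driven groups, which exist only after randomization.
- SAP 4.3 describes patients as being randomized to a treatment group in the DBTP.
- In SAP 14.2 the follow-up row (Week 54, Day 378, Visit 70) stands after the DBTP rows; the OLTP rows end at randomization or early termination with no follow-up row.

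The word overall in the SAP 9.1 sentence attaches to the OLTP alone, and no overall SFU table is described.

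**Step 3. Size.** Inputs: about 1400 enrolled and about 600 randomized (Protocol 9.1); 50% qualifying (SAP 12.0).

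The plan's own enrolment figure first: 600 / 0.50 = 1200, not 1400. Conversely 1400 × 0.50 = 700, not 600. The three figures agree only with a further loss that is not stated: 1200 / 1400 = 0.857, a loss of about 14%. This is a separate, minor inconsistency, but it means the number of never-randomized patients has to be given as a range:
- from the planned counts: 1400 − 600 = 800, and 800 / 1400 = 57.1%
- from the 50% assumption: 1400 − 700 = 700, and 700 / 1400 = 50.0%

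The SFU tables by arm would therefore cover at most 600 / 1400 = 42.9% to 700 / 1400 = 50.0% of enrolled patients.

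**Step 4. Illustration of events affected.** The documents give no follow-up event rate, so these rates are assumptions, and full attendance at follow-up is assumed as well.

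| Assumed share with a follow-up TEAE | Of 700 | Of 800 |
|---|---|---|
| 1% | 7 | 8 |
| 2% | 14 | 16 |
| 5% | 35 | 40 |

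The conclusion does not depend on these rates.

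**Step 5. Newly emergent events in the SFU.** SAP 9.1 defines an SFU NEAE against events present before or at Visit 70, while SAP 14.2 places Visit 70 within follow-up. An event that begins between Visit 69/ET and Visit 70 is thus part of its own reference period, and is not newly emergent unless it worsens or becomes serious. An NEAE row added under that definition would be close to empty, so the reference point has to change first.

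**The case against.** **The group is inferred.** Table shells are not available, and SAP 9.1 uses the term loosely elsewhere: its open-label common-event threshold refers to any treatment group although the OLTP is summarized overall. The weekly and clinically driven wording is a sort order that omits placebo, not a list of columns. This stands as a limit on certainty. The finding concerns the text of SAP 9.1, and the shells may already contain such a column.

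**Nothing is lost.** A reader might infer that these events go unreported. They do not: all patients with adverse events and all deaths are listed, and events up to the ET visit are in the OLTP tables. What is missing is a summary with a denominator.

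**Withdrawal safety is studied elsewhere.** A reader might infer that the safety of stopping rapastinel would be reported only on a selected, stable group. The design does not support that. About 200 patients are randomized from rapastinel to placebo and followed for up to 52 weeks against concurrent rapastinel, with events tabulated by arm. The clinically driven arm also receives placebo at visits rated stable. Patients who relapse in the DBTP enter follow-up too, so the SFU tables are not confined to patients who stayed well.

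**Suicidality.** A reader might infer that suicidality in follow-up goes unsummarized. The other safety analysis sections are redacted or not visible, so this cannot be judged either way.

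**Scope and counts.** SAP 15.0 limits output to an abbreviated report. That is a fair reason to keep tables few, but the SAP has already chosen to produce SFU tables, and they should state whom they cover. The 700 to 800 is a planned count; Protocol 9.3.3 lists withdrawn consent and loss to follow-up among the reasons for leaving, so fewer will attend.

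**Conclusion.** The point holds for the SAP as written. Never-randomized patients enter the SFU, their later events can qualify as TEAEs or TESAEs, and the described SFU summaries have no place for them. By plan this affects about 700 to 800 of 1400 patients, an upper bound on the number actually followed; realised counts and attendance are not given.

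It is a gap in summarization. It does not affect data collection or any efficacy analysis, and the controlled evidence on withdrawal remains in the DBTP. It is worth correcting because at least half of the enrolled patients, all of them last treated with open-label rapastinel, would otherwise have no follow-up rate. The conclusion rests on reading treatment group as double-blind arm, which the SAP's other wording supports but does not state.

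**What to change.** In SAP 9.1:

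1. Add a column, *open-label rapastinel only (not randomized)*, to the SFU overall and common-event tables, covering TEAEs, TESAEs, deaths and related TEAEs.
2. Define its denominator as patients in the Open-label Safety Population who did not enter the DBTP and who did enter the SFU. Counting all non-randomized patients would dilute the percentages with people who were never followed.
3. Add a note that the column is descriptive and is not a randomized comparison with the three arms.
4. Before showing SFU NEAEs in any column, move their reference point from Visit 70 to the last assessment before the SFU starts (Visit 69/ET).

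The cost is SAP wording, one table column and a small amount of programming. No new data are needed.

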**9.7.6.1 Adverse Events**

AEs will be coded by system organ class (SOC) and preferred term using the *Medical Dictionary for Regulatory Activities*.

An AE (classified by preferred term) that occurs during the OLTP or thereafter will be considered a treatment-emergent adverse event (TEAE) if it was not present before the date of the first dose of IP in the OLTP or was present before the first dose of IP in the OLTP and increased in severity during the OLTP or thereafter. If more than 1 AE is reported before the date of the first dose of IP in the OLTP and coded to the same preferred term, the AE with the greatest severity will be used as the benchmark for comparison with the AEs occurring during the OLTP that were also coded to that preferred term.

An AE (classified by preferred term) that occurs during the DBTP of the study will be considered a newly emergent adverse event (NEAE) if the AE was not present before the first dose of the double-blind IP or it was present before the first dose of the double-blind IP and increased in severity during the DBTP. If more than 1 AE is reported before the first dose of the double-blind IP and coded to the same preferred term, the AE with the greatest severity will be used as the benchmark for comparison with the AEs occurring during the DBTP that were also coded to that preferred term. An AE that occurs more than 30 days after the date of the last dose of IP will not be counted as a NEAE.

The number and percentage of patients reporting TEAEs during the OLTP will be tabulated by SOC and preferred term. Similarly, the number and percentage of patients reporting NAEs during the DBTP will be tabulated by SOC and preferred term. The number and percentage of patients in each treatment group reporting TEAEs and NAEs during the DBTP will be tabulated by SOC and preferred term; by SOC, preferred term, and severity; and by SOC, preferred term, and causal relationship to the IP. If more than 1 AE is coded to the same preferred term for the same patient during the same treatment period, the patient will be counted only once for that preferred term using the most severe and most related occurrence for the summarization by severity and by causal relationship to the IP.

The distribution of TEAEs and NAEs by severity and relationship to the IP will be summarized for each treatment group for the DBTP.

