The incidence of common ( $\geq 2\%$  of patients in any treatment group) TEAEs and NAEs during the DBTP will be summarized by preferred term and treatment group and will be sorted by decreasing frequency for the weekly rapastinel group.

An SAE that occurred between the date of the first dose of the open-label IP and 30 days after the date of the last dose of double-blind IP, inclusive, will be considered an on-therapy SAE. The number and percentage of patients who had on-therapy SAEs during the OLTP will be summarized by preferred term and sorted by decreasing frequency. The number and percentage of patients who had on-therapy SAEs during the DBTP will be summarized by treatment group and preferred term and will be sorted by decreasing frequency for the weekly rapastinel group.

The number and percentage of patients who had fatal on-therapy SAEs during the OLTP will be summarized by preferred term and sorted by decreasing frequency. The number and percentage of patients who had fatal on-therapy SAEs during the DBTP will be summarized by treatment group and preferred term and sorted by decreasing frequency for the weekly rapastinel group.

The incidence of TEAEs leading to premature discontinuation of IP during the OLTP will be summarized by preferred term and will be sorted by decreasing frequency. The incidence of TEAEs and NAEs leading to premature discontinuation of IP during the DBTP will be summarized by preferred term and treatment group and will be sorted by decreasing frequency for the weekly rapastinel group.

Listings will be presented for all patients with SAEs, patients with AEs leading to discontinuation, and patients who died (if any).

[REDACTED]

[REDACTED]

[REDACTED]

[REDACTED]

[REDACTED]

[REDACTED]

[REDACTED]

[REDACTED]

[REDACTED]

[REDACTED]

[REDACTED]

[REDACTED]

[REDACTED]

[REDACTED]

[REDACTED]

[REDACTED]

[REDACTED]

[REDACTED]

[REDACTED]

[REDACTED]

[REDACTED]

[REDACTED]

[REDACTED]

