#### 15.0 CHANGES TO ANALYSES SPECIFIED IN PROTOCOL

Analyses and output have been limited to those needed to support the writing of an abbreviated CSR. The major changes to the analyses specified in the original protocol, dated 02MAY2018, are as follows:

• The primary efficacy analysis will be performed via the Kaplan-Meier curve for the cumulative distribution function of time to relapse for each treatment group.

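### SAP 9.1 drops the protocol's by-preferred-term tables of serious, fatal and discontinuation adverse events, so the type of a rare serious event is not tabulated by arm, and SAP 15.0 does not name the change

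*SAP*

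**What the plan says.** **Protocol 9.7.6.1** plans three short displays without a frequency threshold. Each is overall for the open-label treatment period (OLTP) and by arm for the double-blind treatment period (DBTP). For the DBTP:

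- SAEs: "The number and percentage of patients who had on-therapy SAEs during the DBTP will be summarized by treatment group and preferred term".
- Fatal SAEs: "The number and percentage of patients who had fatal on-therapy SAEs during the DBTP will be summarized by treatment group and preferred term".
- Discontinuations: "The incidence of TEAEs and NAEs leading to premature discontinuation of IP during the DBTP will be summarized by preferred term and treatment group".

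It also plans full tables of all treatment-emergent and newly emergent events in the DBTP, which "will be tabulated by SOC and preferred term; by SOC, preferred term, and severity; and by SOC, preferred term, and causal relationship to the IP". The protocol's 2% cut-off belongs to a separate table of common events.

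**SAP 9.1** keeps two kinds of table. The first is a count per category: "The overall number and percentage of patients with TEAEs, NEAEs, death, TESAEs, TEAEs leading to study discontinuation and TEAEs related to study drug". This is overall in the OLTP and by arm in the DBTP and safety follow-up (SFU), with no preferred terms. The second is by preferred term but for common events only. For the OLTP the rule, from the 2% figure on, is "of patients in any treatment group) TEAEs and NEAEs during the OLTP will be summarized overall by preferred term". For the later periods, "the incidence of common TEAEs and NEAEs during the DBTP and during the SFU will be summarized by preferred term and treatment group". SAP 9.1 ends with listings of all patients with adverse events and of patients who died.

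**SAP 15.0** says "Analyses and output have been limited to those needed to support the writing of an abbreviated CSR". It then sets out the major changes from the protocol, and the only one it names is the primary efficacy analysis.

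**The concern.** Safety and tolerability relative to placebo is part of the study objective in both documents. A total per category answers how many patients in each arm had a serious event, but not which events they had. Two arms with similar totals could differ in the kind of event, and a reader of the tables retained in SAP 9.1 would have to assemble that comparison by hand from a patient-level listing.

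The gap touches events that matter in this population. Protocol 9.3.3.1 requires withdrawal for suicide-related adverse events. Those would fall in the discontinuation table and, where serious, in the SAE table, which are two of the displays not carried over.

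Two smaller signs suggest that the cut was not fully reconciled with the rest of the SAP. The OLTP rule refers to any treatment group, although that table is pooled. SAP 14.5 still imputes missing severity for an incidence summary, although SAP 9.1 plans no table by severity.

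**Working it through.** **Step 1. Set the plans side by side.**

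| Display | Protocol 9.7.6.1 | SAP 9.1 |
|---|---|---|
| SAEs | by preferred term, no cut-off | count of patients only |
| Fatal SAEs | by preferred term, no cut-off | count of deaths only |
| Events leading to discontinuation | by preferred term, no cut-off | count of patients only |
| All events by term | yes, plus DBTP severity and causality tables | no |
| Common events (2% or more) by term | yes, DBTP | yes, OLTP, DBTP and SFU |
| Listings | SAEs, discontinuations, deaths | all adverse events, deaths |

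A preferred term therefore reaches a by-term table in SAP 9.1 only if it passes the 2% rule. If it does, the table covers all events under that term and does not show which were serious.

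**Step 2. Turn the cut-off into patients.** The documents give 2% (SAP 9.1), 200 per group and about 1400 enrolled (SAP 12.0). These are planned sizes, so using them is an assumption.

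- DBTP arm: 0.02 × 200 = 4. A term seen in at most 3 patients in every arm, up to 3 × 3 = 9 patients in all, is left out.
- OLTP: 0.02 × 1400 = 28. A term seen in up to 27 patients is left out.
- Smaller arms: 0.02 × 150 = 3, 0.02 × 100 = 2, 0.02 × 50 = 1. At 50 or fewer per arm a single case qualifies.

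**Step 3. Chance that a term reaches the cut-off.** The documents give no SAE rates, so the true rate p is an assumption shown over a range. For one arm of 200,

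q = P(X ≥ 4) = 1 − Σ (k = 0 to 3) C(200, k) p^k (1 − p)^(200 − k).

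At p = 0.01 the four terms are 0.134, 0.271, 0.272 and 0.181. They sum to 0.858, so q = 0.142.

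If all three arms share the rate, the chance that at least one arm qualifies is 1 − (1 − q)³:

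| Assumed rate p | q, one given arm | Any of three arms |
|---|---|---|
| 0.25% | 0.0017 | 0.5% |
| 0.5% | 0.0187 | 5.5% |
| 1% | 0.142 | 36.8% |
| 1.5% | 0.353 | 72.9% |
| 2% | 0.569 | 92.0% |

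In the OLTP, a 1% rate gives 0.01 × 1400 = 14 expected cases against a cut-off of 28. P(X ≤ 27) = 0.9994, so the chance of being tabulated is 0.0006, below 0.1%.

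Under the protocol's three tables the corresponding chance is the chance of one case or more, because there is no cut-off.

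**The case against.** **The reduction is deliberate.** SAP 15.0 gives a reason, the abbreviated report, and claims to itemise only major changes. An abbreviated report can reasonably do without the full system organ class, severity and causality tables. That stands. It explains less well why the short SAE, fatal and discontinuation tables were removed without being named.

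**No event is lost.** This also stands. A reader might infer that rare serious events vanish from the report. They do not. Each adds to the by-arm totals, and the listing of all adverse events is broader than the protocol's SAE and discontinuation listings. The Data and Safety Monitoring Board reviews safety data separately.

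**Other outputs may show event type.** A reader might infer that two arms with different serious events would look identical in every planned table. The documents do not support that. The visible SAP moves from 9.1 to 11.0, so later safety sections cannot be read. Suicide risk is a relapse criterion and feeds the by-arm Kaplan-Meier curves, and SAP 5.0 tabulates reasons for discontinuation by arm. Against this, SAP 9.1 reads without a break from definitions to listings, so it is unlikely, though not excluded, that a by-term SAE table sits elsewhere.

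**The size depends on numbers not in the documents.** That stands too. The rates are assumed and the arm sizes are planned. A reader might infer that a 3 v 0 split can never be tabulated. At 200 per arm it is left out only if the third arm also stays below 4, and in arms of 150 or fewer, 3 patients already meet the cut-off.

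**The OLTP wording is a slip.** It is minor, since the table is pooled and the intended denominator can be guessed. It is worth correcting while the section is open.

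**Conclusion.** The point holds for by-type tabulation, not for reporting as such. As far as SAP 9.1 can be read, three protocol tables without a cut-off have become category totals plus by-term tables restricted to 2% or more, and SAP 15.0 covers this only by its general remark on the abbreviated report.

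If arms reach the planned 200, a term occurring at 0.5% or below will usually be missing from the by-arm table of event types, and at 1% it is missing more often than not (about 63%, from 1 − 0.368). The effect shrinks in smaller arms and disappears at 50 or fewer per arm. Even there, serious events would not be separated from non-serious ones under the same term.

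This rests on the planned sizes, on the assumed range of rates, and on there being no by-term SAE table in SAP text that is not visible. It does not affect the efficacy analysis. It should be corrected because the correction is cheap and the comparison with placebo is a stated objective.

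**What to change.** In SAP 9.1:

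- Restore tables by preferred term, without a frequency cut-off, for treatment-emergent SAEs, fatal treatment-emergent SAEs and adverse events leading to discontinuation. Present them overall for the OLTP and by treatment group for the DBTP and SFU.
- Keep the 2% cut-off for the common-event tables only. For the OLTP, state that it applies to the pooled total.

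In SAP 15.0, name every protocol safety table that is deliberately dropped, such as the breakdowns by severity and causality, and give the reason.

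The cost is about three standard tables per period, from adverse event data already collected and coded, plus a few lines of SAP text. The downside is a slightly longer abbreviated report.
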